5.9.1. Permitted Concomitant Therapies

The following medications and treatment are permitted in this study after Day 1:

- Non-steroidal anti-inflammatory drugs (NSAIDs), acetaminophen, or antihistamines may be used after dosing if the subject has a fever ≥ 38.0°C (100.4°F) or if the subject has significant nasal pain, myalgia, or headache. NSAIDs or acetaminophen should not be taken prophylactically and in the event of use should be documented in the eDiary.
- Low-dose aspirin.
- Medications used by the subject to treat stable chronic health conditions, which were reported previously during the screening visit, if use of those medications does not interfere with assessments of study safety and immune responses.

5.9.2. Prohibited Concomitant Therapies

The following medications are not permitted in the study:

- Concomitant use of any new (not previously used by subject or dosage changed within past month) prescription (except for contraceptive pills, implants, transdermal or injections), new vitamins or new dietary supplements. Over-the-counter (OTC) medications are discouraged but allowed for 7 days prior to IP vaccination and continuing until 7 days after last vaccination. Any such use of OTC must be recorded in the source documents along with the associated AE (if applicable).
- Any licensed vaccine, other than the study-provided licensed influenza vaccine, during the 28 days following Visit 01 or another investigational vaccine or investigational drug during the study period.
- Receipt of blood/plasma products or immunoglobulin during the study period.

Any medication that is not covered by the permitted and non-permitted medication sections can be allowed at the discretion of the Investigator and documented on eCRF.

6. ASSESSMENTS

6.1. Timing of Assessments

An overview of the timing of treatments and assessments is given in the Schedules of Events (Section 6.1.1). The Schedule of Events and visits for IP administration is provided in Table 2 and the schedule and visits for QIV administration is provided in Table 3.

When visit assessments are planned at the same time point in the study, the order of assessments should be in order of less invasive to more invasive. For example, during the randomization visit, vitals, medical history, pregnancy testing and drug testing should be conducted before blood work and subsequent nasal swab.

Prior to all on-site visits, the site will assess the subject's health status in accordance with local policies to evaluate whether subject is fit to attend the clinic. This may include a phone call or email, etc. with questions regarding Covid-19-related symptoms, known exposure to Covid-19 within past 14 days and/or subject having confirmed positive test for Covid-19. A subject deemed not suitable should not attend the site and the PI or designee should contact the Medical Monitor to discuss subject study status.

6.1.1. Schedules of Events

Table 2: Schedule of Events – IP Administration

Study Visit Number	V00	V01	V02	V03	Early Term ⁵
Study Day Post-First Dose	Days -28 to -1	Day 1	Day 8 ±1	Day 29 ±3	
Informed Consent	X				
Inclusion/Exclusion	X	X^2			
Demography	X				
Physical exam - including height/weight	X^{1}				
Limited physical exam ⁷		$X^{2,3}$	X	X	X
Medical history	X	χ^2			
Vital signs (BP, HR & body temp)	X	X ^{2, 3}	X	X	X
Hematology & Chemistry ⁴	X	2, 10			χ^9
Urinalysis including drugs of abuse	X				
Urine Pregnancy (females, child-bearing potential)	X	χ^2			X^9
Testing for HIV, HBV, HCV	X				
Nasal swab – immunogenicity		X ^{2, 6}		X^6	χ^6
Nasal swab - respiratory agent(s)	X ¹²	$X^{2,13,14}$	X ^{12,14}		
Serum collection (HAI, MN, NAI and ELISA)	X ¹¹			X	X
PBMC collection (50 mL for CMI) and plasma		χ^2		X	
Blood collection (5 mL for RNA ¹⁵)		χ^2	X		
Investigational dose administration		X			

Study Visit Number	V00	V01	V02	V03	Early Term ⁵
Study Day Post-First Dose	Days -28 to -1	Day 1	Day 8 ±1	Day 29 ±3	
Dispense & train on eDiary and thermometer use 8		X	X		
Review eDiary data		←	X→		X
AEs/Con meds	X	$X^{2,3}$	X	X	X
SAEs	X	X^2	X	X	X

AE=adverse events; BP=blood pressure; CMI=cell-mediated immunity; Covid-19=coronavirus disease of 2019; ELISA=enzyme-linked immunosorbent assay; HAI=hemagglutination inhibition; HBV=hepatitis B virus; HCV=hepatitis C virus; HIV=human immunodeficiency virus; HR=heart rate; IP=investigational product; MN=microneutralization; NAI=neuraminidase inhibition; PBMC=peripheral blood mononuclear cells; PCR=polymerase chain reaction; PI=Principal Investigator; RNA=ribonucleic acid; SAE=serious adverse events; temp=temperature; term=termination; V=visit; WBC=white blood cell count.

- 1 Complete physical is required; neurological, rectal and gynecological exams do not need to be performed unless clinically indicated.
- 2 Prior to dosing.
- 3 At approximately 15 minutes after dosing.
- 4 Laboratory tests to establish baseline status as listed in Appendix 3 for hematology and biochemistry.
- 5 Early Term visit is applicable if a subject does not complete the study within 28 days after IP dose administration. eDiary to be reviewed, if within 7 days of dose administration.
- 6 Collect sample prior to swab for respiratory agents.
- 7 Specifically includes the nares (including edema), throat, and lungs (including evaluation for wheezing) up to and including Day 29. A targeted physical examination may be performed on other body systems if indicated based on review of interim medical history or subject symptoms as observed by site or by PI.
- 8 Dispense on day of dose then ongoing review for 7 additional days following vaccine administration using electronic capture and internet-based portal. If subject does not populate eDiary every 24-hours, the site will contact them for follow-up and document the contact in subject's source.
- 9 Sample collected if subject presents with AE requiring laboratory assessment.
- 10 If screening blood collection was greater than 28 days prior to Day 1 then laboratory assessments are to be repeated to establish baseline.
- 11 Serum at screening will be tested for HA immunology and will be considered baseline for the subject. A prescreen titer, collected under a separate site-specific protocol will be used to assess entry criteria.
- 12 PCR Test for Covid-19.
- 13 V01 sample to be tested by multiplex PCR test for abbreviated list of respiratory pathogens including Covid-19, Flu A, Flu B and RSV. Additional swabs may be collected at unscheduled visits, if the subject presents with respiratory symptoms that warrant additional testing; in such case a full respiratory panel is to be performed. 14 Collect, store, then batch test.
- 15 RNA analyzed for gene expression (no genetic testing of inherited diseases will be done)

Table 3: Schedule of Events – QIV Administration

Study Visit Number	V04 ¹	V05
Study Day Post-QIV Dose	Day 1	Day 29 ±7
Safety check	X^2	
Limited physical exam ³	$X^{2,4}$	X
Vital signs (BP, HR & temp)	X^2	X
Nasal swab – immunogenicity	X^5	X
Serum collection (HAI, MN, NAI and ELISA)	X^2	X
Administer licensed influenza vaccine 6	X	
AEs/Con meds	χ^2	X
SAEs	X^2	X

AE=adverse events; BP=blood pressure; ELISA=enzyme-linked immunosorbent assay; HAI=hemagglutination inhibition; HR=heart rate; QIV= quadrivalent influenza vaccine; IP=investigational product;

MN=microneutralization; NAI=neuraminidase inhibition; PI=Principal Investigator; QIV=quadrivalent inactivated vaccine; SAE=serious adverse events; temp=temperature; term=termination; V=visit.

- 4 At approximately 15 min after dosing.
- 5 Sample collected for secretory IgA immune response by ELISA
- 6 Licensed vaccine supplied to site by Sponsor; product used will be age-appropriate for the subject

6.1.2. Screening Period

In a private, individual setting, subjects will be given a full explanation of the nature of the study and written informed consent (Institutional Review Board [IRB] approval will be obtained before any study-related assessment) will be carried out. Group consenting will not be permitted and subjects requiring a Legally Authorized Representative may not participate in this study.

Screening for eligible and consenting subjects will be performed within 28 days prior to randomization/IP administration. Subjects will be re-confirmed for eligibility on Day 1 (V01) prior to dose administration. Chemistry and hematology at V00 will serve as eligibility and baseline values unless collected more than 28 days prior to V01. In such case the lab tests will be redone to establish baseline only.

Subjects will have been consented and prescreened for influenza serosusceptibility under a separate, site-specific IRB-approved informed consent form (ICF). The prescreening protocol and related ICF will be made available upon request by the Sponsor.

At screening, subjects will be asked to attend the clinical site to have assessments performed as indicated in the Schedule of Events (Table 2).

¹ V03 from IP dosing schedule and V04 from QIV dose schedule may be combined on same day if V04 occurs at least 28 days after V01. In such case, activities do not need to be duplicated during the visit.

² Prior to dosing. Subjects will be assessed for any known reactions to licensed influenza vaccines.

³ Specifically includes the dermal injection site. A targeted physical examination may be performed on other body systems if indicated based on review of interim medical history or subject symptoms as observed by site or by PI.

All results from the screening procedure needed to evaluate eligibility, including the clinical laboratory results, must be available prior to study vaccination on Day 1. Any abnormal assessment at the screening visit will be assessed according to its clinical relevance, and if found clinically significant, the subject will not be included in the study.

During the screening period, the following procedures and assessments will be carried out for each subject to determine their eligibility for participation in the study:

- Obtain informed consent prior to any procedures being performed
- Record demographics
- Confirm eligibility criteria for enrollment and vaccination
- Obtain medical history
- Record concomitant medications
- Perform complete physical examination (neurological, rectal and gynecological exams do not need to be performed unless clinically indicated), including height and weight
- Vital signs (blood pressure, heart rate, and body temperature)
- Collect urine for dipstick pregnancy test (applicable females only)
- Collect nasal swab for Covid-19 testing
- Collect blood for serology for HIV, HBV and HCV
- Collect blood for serum chemistry and hematology
- Collect blood for immunogenicity assays
- Urinalysis (dipstick) and urine screen for drugs of abuse
- Record any concomitant therapy/medically attended AEs/SAEs after signing of consent

Beginning at the screening visit and at subsequent visits subjects will be instructed on Covid-19 best practices including wearing a mask in public spaces whether indoors or outdoors, distancing from people outside of their household, frequent washing of hands, etc. At each visit, subjects will be asked a series of scripted questions to evaluate their exposure to Covid-19 and results will be documented in the source.

Unscheduled visits may be planned (up to Day 28) to assess, confirm, and follow-up on out-of-range clinical laboratory test, or vital sign values that determine a subject's eligibility, or in case of a positive urine drug screen. The result of the retest will be considered for subject eligibility. Findings made during unscheduled visits should be reported in the eCRF system.

A record of the number of screening failures and the reasons for screening failure will be captured in a study file. Data for subjects who fail screening or who are not randomized into the study will not be included in the study database. The failure details will be documented in a study file maintained by the site.

6.1.3. Licensed Vaccine Visit

Subjects will undergo a safety check prior to dose administration of the licensed influenza vaccine product to confirm there are no contraindications to the licensed vaccine as per the package insert. Subjects will be excluded from dosing if they have ever had a severe allergic reaction to eggs or egg products or after getting any influenza vaccine.

6.1.4. Early Termination Visit

Subjects who withdraw consent will be asked to attend the clinic for safety evaluation as described in Early Termination assessments (Table 2).

Early Termination assessments should be completed within 7 (\pm 3) days of discontinuation for subjects who discontinue from the study. The following assessments are to be performed:

- Limited physical examination
- Vital signs (blood pressure, heart rate, and body temperature)
- Collect blood for serum chemistry and hematology
- Collect urine for pregnancy test (applicable females only)
- Collect blood sample for immunogenicity assays
- Nasal swab mucosal IgA
- Review eDiary
- Record concomitant therapy/AEs/SAEs

6.1.5. Unscheduled Visits

Unscheduled visits can be planned:

- To obtain additional information to ensure safety to the subject. Additional blood and urine samples may be taken at the discretion of the Investigator.
- To obtain a nasal swab for assessment of potential infection with influenza, SARS-CoV-2 or other respiratory agents (at discretion of PI). If a subject presents within 7 days of IP vaccination with symptoms such as fever, upper respiratory illness, nephritis/cystitis, conjunctivitis or diarrhea, regardless of the severity of the symptoms, an additional nasal swab(s) should be collected and/or analyzed outside of the defined time points. Possible infection with respiratory pathogens (including SARS-CoV-2) may be evaluated by use of a commercial, qualitative and multiplexed polymerase chain reaction (PCR) test for detection of upper respiratory tract pathogens; i.e., the full respiratory panel test in Appendix 3.
- To assess, confirm, and follow-up on out-of-range clinical laboratory test, or vital sign values that will determine a subject's eligibility, or in case of a positive drug screen.
 - The result of the retest will be considered for subject eligibility.

Findings made during unscheduled visits should be reported in the eCRF.

6.2. Study Assessments

6.2.1. Clinical Evaluations

6.2.1.1. Medical History

A complete medical history will include a review of all major body systems. Significant past and present medical history will be obtained by interview during the screening visit.

6.2.1.2. Concomitant Medications

Details of prescription and over-the-counter medications (including vitamins) currently used will be recorded during the screening visit. Concomitant medications will be reviewed at each visit and any new medications will be documented on the eCRF.

6.2.1.3. Demographics

Demographics will be obtained during screening only. Demographics will include the age and race and ethnicity as described by the subject.

6.2.1.4. Physical Examination

6.2.1.4.1. Complete Physical Examination

A complete physical examination will be performed for each subject at the time points specified in the Schedules of Events (Table 2 and Table 3). It will include collection and recording of subject's height and weight. The examination will consist of assessment of the following organs/systems:

- Head
- Eves
- Ears, nose, throat
- Neck
- Cardiovascular
- Chest
- Respiratory
- Abdomen
- Genitourinary only if clinically indicated
- Extremities
- Musculoskeletal
- Nervous system only if clinically indicated
- Dermatological
- Other conditions of note

6.2.1.4.2. Limited Physical Examination

A limited physical exam will be performed for each subject at the time points specified in the Schedules of Events (Table 2 and Table 3). The examination will include the nares (including edema), throat, and lungs (including evaluation for wheezing). A targeted physical examination may be performed on other body systems if indicated based on review of interim medical history or subject symptoms as observed by site or by PI.

6.2.1.5. Vital Signs

Vital signs include oral temperature (°C), blood pressure (mmHg), pulse rate (beats per minute). Vital signs will be obtained at the time points specified in the Schedules of Events (Table 2 and Table 3). Blood pressure will be measured from the subject's arm after the subject has been seated or semi-recumbent for approximately 5 minutes with the arm supported at the level of the heart. Blood pressure will be recorded to the nearest mmHg.

6.2.1.6. Urine Samples

Urine samples for the determination of pregnancy for women of childbearing potential, drug screening, and urinalysis will be collected at the time points specified in the Schedules of Events – IP Administration (Table 2).

A midstream urine sample will be collected for baseline urinalysis by dipstick for specific gravity, pH, glucose, protein, ketones, bilirubin, urobilinogen, nitrite, leukocyte esterase, and occult blood. Results are obtained by comparing the color block on the canister to those on the reagent strips where the color blocks enclosed by the black box are considered Normal.

If dipstick urinalysis is Abnormal/positive for protein, blood, nitrite and/or leukocyte esterase, a microscopic examination for white blood cells (WBC), red blood cells (RBC), bacteria, casts, and epithelial cells will be performed. Crystals, casts, and bacteria will only be reported if present.

A urine drug of abuse screen will be performed for detection of opiates, phencyclidine (PCP), cocaine and amphetamines.

6.2.2. Bioanalysis

Blood samples for determination of the concentration of analytes specified in Appendix 3 will be analyzed by a qualified vendor under the responsibility of the Sponsor, using validated analytical methods.

The Investigator must review the laboratory report, document this review, and record any change occurring during the study he considers to be clinically relevant in the AE section in the electronic data capture (EDC) system. Laboratory values outside the normal range will be flagged and their clinical relevance as an AE will be assessed by the Investigator. Laboratory values which are Grade 3 or higher based on the grading scales in Appendix 4 will be reported to the Sponsor within 24 hours of Investigator awareness, and assessment of clinical relevance will be reviewed by the Medical Monitor.

The laboratory analysis will be carried out following the principles of Good Laboratory Practice (GLP) regulations.

6.2.3. Adverse Events

Adverse events will be monitored regularly from informed consent until Visit 05 (28 days after QIV administration). At regular intervals during the study, subjects will be asked non-leading questions to determine the occurrence of any AEs. All AEs reported spontaneously during the study will be recorded as well. Solicited and unsolicited signs and symptoms will be reported as AEs after review by the Investigator or designee, either separately using the corresponding Medical Dictionary for Regulatory Activities (MedDRA) terminology of the sign or symptom or combined using the appropriate term. For example, a subject who reported concurrent cough, runny nose, and sneezing assessed by the Investigator as unrelated to vaccine should have those symptoms grouped as a syndromic diagnosis (URI), with the severity based on the most severe AE/symptom. Therefore, as a secondary presentation, subjects with 3 or more concurrent unrelated AEs of cough, runny nose/rhinorrhea, sneezing, sore throat, itchy throat, itchy eyes, congestion, nasal irritation, hoarseness, headache, body aches/myalgia, tiredness/fatigue, malaise, and fever will have those AEs grouped as URI.

For detailed definitions and reporting procedures of AEs, see Section 9.

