7.3. Halting Rules

Vaccination of subjects with the Study IP will be suspended until after blinded review of safety data by the SRC if any of the following halting rules are met:

- 1. One or more subjects experience a Grade 4 AE assessed as related to IP.
- 2. Three or more subjects within an age group experience the same Grade 3 AE assessed as related to IP.
- 3. One or more subjects experiences an SAE assessed as related to IP.
- 4. One or more subjects has laryngospasm, bronchospasm, or anaphylaxis associated with the study IP within 72 hours after administration assessed as related to IP.

Any AE or SAE that falls into the above criteria for suspending or terminating study vaccinations must be reported by the Investigator to the Sponsor immediately (within 24 hours).

In the case of AEs meeting the above criteria, the SRC will be convened as quickly as possible, but no later than 3 days after the notification of the event(s). After review of the safety data the SRC will make a recommendation to the Sponsor whether to resume, suspend, or terminate the study. The Sponsor will communicate a decision to suspend or terminate the study to the Investigators. Upon request, the SRC may be provided with an unblinded data set for review.

Subsequent review of serious, unexpected, and related AEs by the Medical Monitor, SRC, IRB, the Sponsor(s), or the Regulatory Agency may also result in suspension of further trial interventions/administration of study product at a site. The FDA and study Sponsor(s) retain the authority to suspend additional enrollment and study interventions/administration of study product for the entire study, as applicable.

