9.3. Causality Assessment

The clinician's assessment of an AE's relationship to test article (vaccine or placebo) is part of the documentation process, but it is not a factor in determining what is or is not reported in the study. If there is any doubt as to whether a clinical observation is an AE, the event should be reported. All AEs must have their relationship to study product assessed using the terms related or not related. In a clinical trial, the study product must always be suspect. To help assess, the following guidelines are used.

Related – There is a reasonable possibility that the study product caused the AE. Reasonable possibility means that there is evidence to suggest a causal relationship between the study product and the AE.

Not Related – The AE is not related to the study product if there is evidence that clearly indicates an alternative explanation. If the subject has not received the study product, the timing of the exposure to the study product and the onset of the AE are not reasonably related in time, or other facts, evidence or arguments exist that strongly suggest an alternative explanation, then the AE is not related.

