9.5. Recording of Adverse Events

All (S)AEs occurring during the clinical investigation must be documented in the source documents and eCRF.

Whenever possible, diagnoses should be given when signs and symptoms are due to a common etiology (e.g., cough, runny nose, sneezing, sore throat, and head congestion should be reported as "upper respiratory infection"). Investigators must record their opinion concerning the relationship of the (S)AE to the study drugs in the EDC System. All measures required for (S)AE management must be recorded in the source documents and reported according to Sponsor's instructions.

All AEs occurring at any time during the study (including the in-person follow-up period) will be followed by the Investigator until satisfactory resolution (e.g., value back to baseline value) or stabilization or until final database lock. If necessary, to obtain additional information to ensure safety of the subject, additional blood and urine samples may be taken at the discretion of the Investigator. Certain long-term AEs related to therapy cannot be followed until resolution within the setting of this study. In these cases, follow-up will be the responsibility of the treating physician.

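### Protocol 6.2.3 and 9.5 give different rules for combining symptoms into URI, and the 6.2.3 list can yield a URI with no respiratory symptom

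*Protocol*

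**What the plan says.** Protocol 6.2.3 contains three statements on combining symptoms.

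- The investigator may report signs and symptoms "either separately using the corresponding Medical Dictionary for Regulatory Activities (MedDRA) terminology of the sign or symptom or combined using the appropriate term".
- In its worked example, concurrent symptoms judged unrelated to vaccine should be grouped as URI, graded by the worst symptom.
- It then derives a rule for a secondary display: "subjects with 3 or more concurrent unrelated AEs of cough, runny nose/rhinorrhea, sneezing, sore throat, itchy throat, itchy eyes, congestion" and other listed terms are grouped. The list ends "headache, body aches/myalgia, tiredness/fatigue, malaise, and fever will have those AEs grouped as URI".

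Protocol 9.5 asks for a diagnosis whenever possible if symptoms share an etiology. Its example is that "cough, runny nose, sneezing, sore throat, and head congestion should be reported as 'upper respiratory infection". It states no relatedness condition and no minimum number of symptoms.

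Two other sections decide what follows from the choice. Protocol 9.3 rates causality against the investigational product: "The clinician's assessment of an AE's relationship to test article (vaccine or placebo) is part of the documentation process". Halting rule 2 in Protocol 7.3 is met when "Three or more subjects within an age group experience the same Grade 3 AE assessed as related to IP".

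SAP 9.2 tabulates treatment-emergent and related AEs by system organ class and preferred term. SAP 9.6 lists events that meet the halting criteria. The SAP mentions no URI grouping and does not say whether grouped or ungrouped terms feed these outputs.

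**The concern.** Nasal and throat symptoms are among the reactions solicited after this intranasal live-virus vaccine. If the AE record of such a reaction depends on which section a site follows, sites and arms are not counted on one basis. A single infection term and several symptom terms fall under different preferred terms, may carry different causality ratings, and may or may not match as the same event under halting rule 2. The 6.2.3 list raises a second, smaller problem. It can call a set of systemic symptoms a respiratory infection, which matters most after QIV, where no diary is kept and safety is the first secondary objective.

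**Working it through.** No figure in the plan bears on this point, so the check is a comparison of texts and a count.

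**1. The rules side by side**

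| Feature | 6.2.3 example | 6.2.3 list rule | 9.5 |
|---|---|---|---|
| Unrelated status required | yes | yes | no |
| Minimum number of symptoms | none stated (three in the example) | three | none stated |
| Common etiology required | not stated | not stated | yes |
| Where applied | AE reporting | secondary display | AE recording |
| Severity of combined term | worst symptom | not stated | not stated |

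Because 6.2.3 also permits separate reporting and refers to Section 9 for reporting procedures, two compliant sites can record one reaction differently.

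**2. Overlap with solicited reactions.** Protocol 6.2.4.1 and 6.2.4.2 solicit runny nose, nasal congestion, cough and sore throat. Taking head congestion as nasal congestion, 4 of the 5 symptoms in the 9.5 example are solicited; only sneezing is not.

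**3. Effect on related-AE and halting counts**

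- 6.2.3 list rule: every AE it groups is already unrelated, so it removes 0 events from counts of related events.
- 9.5, combined term rated not related: the event leaves the related counts.
- 9.5, combined term rated related, mixed practice: three subjects in one age group have related Grade 3 congestion. If two are recorded as congestion and one as URI, the largest matching count is 2 rather than 3.
- 9.5, combined term rated related, uniform practice: three subjects have related Grade 3 congestion, cough and sore throat respectively, each with milder accompanying symptoms. Recorded separately, the largest matching Grade 3 count is 1. Recorded as URI at worst-symptom severity, it is 3.

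The direction is therefore not fixed.

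**4. Illustration of one direction, on assumed inputs.** Table 1 of the protocol gives 10 + 60 = 70 active subjects aged 65-85. Let p be the true rate of one related Grade 3 term and f the share recorded instead as an unrelated URI. Then P(X ≥ 3), with X ~ Binomial(70, p(1 − f)), is:

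| p | f = 0 | f = 25% | f = 50% |
|---|---|---|---|
| 2% | 0.165 | 0.088 | 0.033 |
| 5% | 0.686 | 0.491 | 0.255 |
| 10% | 0.976 | 0.904 | 0.686 |

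Neither p nor f is in the documents. The table shows sensitivity, not an expected effect.

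**5. URI with no respiratory term.** The 6.2.3 list has 14 terms, giving C(14,3) = 364 triples. Five terms are systemic (headache, myalgia, fatigue, malaise, fever), giving C(5,3) = 10 triples, or 10/364 = 2.7%. These are counts of word combinations, not event frequencies.

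**6. After QIV.** Protocol 8.3 confines the eDiary to the period after IP. Since 9.3 rates causality against vaccine or placebo, a systemic reaction to QIV can be rated not related and then meet the list rule. Halting rule 2 and the other halting rules count only IP-related events, so those counts do not change.

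**The case against.** A reader might infer that the 14-term list lets vaccine reactions drop out of the related-AE and halting counts. The documents do not support that. The list acts after causality, on unrelated events only, and only in a secondary display. Nor do QIV reactions leave the halting counts: those rules cover IP-related events, so QIV reactions were never in them.

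A reader might also infer that the URI label itself makes an event unrelated. It does not. Protocol 9.3 requires evidence that clearly points to another explanation, treats the product as always suspect, and requires a rating for every AE, including a combined one. The common-etiology condition in 9.5 calls for judgement, and the PCR swabs in 6.1.5 and Appendix 3 help separate infection from reaction.

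The solicited endpoint is protected too. Protocol 2.2.1 takes it from the eDiary, and SAP 9.2.1 summarises it by symptom without URI grouping.

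All of this stands, and it limits the point. It does not remove the conflict between the sections:

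- The halting rules and related-AE tables need a causality rating, which the diary in Appendix 1 lacks.
- SAP 9.2 makes reporting a diary symptom as an AE discretionary and does not reconcile the two sources.
- Seven of the 14 listed terms are not diary items: sneezing, itchy throat, itchy eyes, nasal irritation, hoarseness, fatigue and malaise.
- Nothing in 9.5 makes combining depend on a PCR result or on a prior rating for each symptom.

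**Conclusion.** The point holds as an inconsistency in AE recording that should be resolved. Sections 6.2.3 and 9.5 allow different AE records for the same nasal reaction. The related-AE tables and the matching of events under halting rule 2 can move either way as a result. The size cannot be derived from the documents, because it depends on how sites combine symptoms and how they rate the combined term.

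The list problem is confined to the secondary URI display. It assumes that unrelated means unrelated to IP, as 9.3 suggests; the 6.2.3 example speaks only of the vaccine and is less clear. The SAP plans no such display at present, so the problem arises only if the 6.2.3 rule is carried out as written.

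**What to change.** - **Protocol 9.5 and 6.2.3:** use one rule. Assess causality and severity for each symptom before any combining, keep the component terms in the record, and use URI only for symptoms judged unrelated.
- **6.2.3 list:** require at least one respiratory-tract term, and exclude events attributed to QIV. The documents do not show a separate field for attribution to QIV, so the eCRF may need one.
- **SAP 9.2 and 9.6:** define the URI table as secondary, and state that the main AE tables, related-AE tables and halting-event listing use ungrouped terms. No halting threshold changes.

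The cost is wording in two protocol sections and the SAP, one additional table, and more AE rows for a subject with a true cold. Where sites have already merged symptoms, a program cannot separate them from the AE term alone. Those records would need a query or a listing of all AEs recorded as URI.
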